# **Abbreviations**

Abbreviations	Definitions					
ABC	Advanced breast cancer					
AE	Adverse event					
AESI	Adverse event of special interest					
AI	Aromatase inhibitor					
AKT	Protein kinase B					
ALT	Alanine aminotransferase					
ANC	Absolute neutrophil count					
aPTT	Activated partial thromboplastin time					
ASCO	American Society for Clinical Oncology					
AST	Aspartate aminotransferase					
AUC	Area under the curve					
$AUC_t$	Area under the concentration-time curve					
BTC	Betacellulin					
$C_{avg}$	Average serum concentration					
CBC	Complete blood count					
CFR	Code of Federal Regulations					
CI	Confidence interval					
CL	Clearance					
$C_{max}$	Maximum serum concentration					
CMH	Cochran-Mantel-Haenszel (test)					
$C_{\min}$	Minimum serum concentration					
CNB	Core needle biopsy					
CNS	Central nervous system					
CR	Complete response					
CRF	Case report form					
CRO	Contract research organization					
CT	Computed tomography					
CTCAE	Common terminology criteria for adverse events					
CTG	Cell TiterGlo					
DMC	Data Monitoring Committee					
EC	Ethics Committee					
ECG	Electrocardiogram					
ECHO	Echocardiogram					
ECOG (PS)	Eastern Cooperative Oncology Group (performance status)					
eCRF	Electronic case report form					
EGFR	Epidermal growth factor receptor					
ER	Estrogen receptor					
ErbB	Epidermal growth factor family of receptor tyrosine kinases					
ESR1	Estrogen receptor alpha					
FDA	Food and Drug Administration					
FFPE	Formalin-fixed, paraffin-embedded					
FGF	Fibroblast growth factor					
FL-IHC	Fluorescence-based immunohistochemistry					
FNA	Fine needle aspiration					
g	Gram					
GCSF	Granulocyte-colony stimulating factor					
GCP	Good Clinical Practice					
GnRH	Gonadotropin-releasing hormone					

GR Grade

HAHA Human anti-human antibodies

HER2 Human epidermal growth factor receptor 2

HGF Hepatocyte growth factor

HIPAA Health Insurance Portability and Accountability Act

HR Hazard ratio HRG Heregulin

HR-positive Hormone receptor positive IB Investigator's Brochure

ICH International conference on harmonization

Ig Immunogenicity

IGF Insulin-like growth factor

IGF-1R Insulin-like growth factor 1 receptor

IHC Immunohistochemistry
 INR International normalized ratio
 IRB Institutional Review Board
 IRR Infusion-Related Reaction
 ISH In-situ hybridization

ITT Intent to treat

MITT Modified Intent to treat

IV Intravenous

IWRS Interactive web response system

kg Kilogram

LDH Lactate dehydrogenase LH Luteinizing hormone

LVEF Left ventricle ejection fraction mBC Metastatic breast cancer

mcg Micrograms

MedDRA Medical Dictionary for Regulatory Activities

mg Milligram

mOC Metastatic ovarian cancer

mL Milliliter

MRI Magnetic resonance imaging
MTD Maximum tolerated dose
mTOR Mammalian target of rapamycin

MUGA Multiple gated acquisition scan NCI National Cancer Institute

NRG Neuregulin

NSAID Non-steroidal anti-inflammatory drug

NSCLC Non-small cell lung cancer NYHA New York Heart Association ORR Objective Response Rate

OS Overall survival

p.o. Per os (oral administration)

PD Progressive disease
PE Pulmonary embolism

PET-CT Positron emission tomography - computed tomography

PFS Progression free survival PgR Progesterone receptor

PI3K Phosphatidylinositol-3-kinase

PK Pharmacokinetic(s)
PR Partial response
PTT Prothrombin time

QD Every day
Q1W Every week
Q2W Every 2 weeks
Q3W Every 3 weeks
QW Weekly

RANKL Receptor activator of nuclear factor kappa-B ligand

RBC Red blood cell

RECIST Response evaluation criteria in solid tumors

RNA Ribonucleic acid

RNAi Ribonucleic acid interface

RT-PCR Reverse transcription polymerase chain reaction

SAE Serious adverse event SAF Safety Population SAP Statistical Analysis Plan

SD Stable disease

SERD Selective estrogen receptor disruptor SERM Selective estrogen receptor modifier SmPC Summary of Product Characteristics

TCGA The Cancer Genome Atlas TKI Tyrosine kinase inhibitor

Tmax Time to maximum serum concentration

TTP Time to Progression ULN Upper limit of normal

US United States

USP United States Pharmacopeial Convention VDss Volume of distribution at steady state

WBC White blood cell

# **Study Synopsis**

CDONICC	1.6 1.70						
SPONSOR:	· · · · · · · · · · · · · · · · · · ·						
	[name]						
	[name]						
	[name]						
PROTOCOL TITLE:	A Double-blind, Placebo-controlled, Phase 2 trial of Seribantumab Plus						
	Fulvestrant in Postmenopausal Women with Hormone Receptor-positive,						
	Heregulin Positive (HRG+), HER2 Negative Metastatic Breast Cancer						
	Whose Disease Progressed After Prior Systemic Therapy						
TRIAL LOCATION:	North America and Europe						
PROTOCOL NUMBER:	MM-121-02-02-10						
	Primary Objective:						
	• To determine whether the combination of seribantumab + fulvestrant is more effective than placebo + fulvestrant based on investigator assessed Progression Free Survival (PFS) in HRG positive patients (defined as HRG ISH score of ≥ 1+)						
	Secondary Objectives:						
STUDY OBJECTIVE(S):	
 
To determine whether the combination of seribantumab + fulvestrant is more effective than placebo + fulvestrant in HRG positive patients for the following clinical outcome parameters:         
 
Time to Progression (TTP)
 
Overall Survival (OS)
 
 
 
						
	
 
Objective Response Rate (ORR) based on RECISTv1.1
 
To describe the safety profile of seribantumab in combination with fulvestrant
 
To characterize the pharmacokinetic (PK) profile of seribantumab when given in combination with fulvestrant and of fulvestrant when given in combination with seribantumab
 
						
	
 
Exploratory Objectives:
 
To assess the correlation for HRG expression between fresh tissue biopsies and archival samples where available
 
						
	This is a multi-center, randomized, double-blind, placebo-controlled Phase 2 study of seribantumab or placebo with fulvestrant in patients with ER/PR positive, HER2 negative, metastatic, unresectable breast cancer whose tumor expresses HRG as measured by RNA in-situ hybridization (RNA-ISH).						
STUDY DESIGN:	Following signing informed consent for biomarker testing and evaluation of initial eligibility criteria, all patients will provide a tissue sample (which meets the requirements for collection and processing as outlined in the study lab manual) to the designated central lab facility for HRG testing. If adequate tissue is not available, patients should undergo a tumor biopsy to acquire the necessary tissue for HRG testing. For these procedures, investigators are asked to choose an easily accessible tumor lesion to minimize any possible risk associated with the collection of the tissue. As a general guideline, if the selected procedural location of the biopsy has an established serious complication rate of >2% at the institution completing						

the procedure, this is considered a high risk procedure and should be avoided. Upon receipt of a tissue sample at the central lab, the investigational site will be informed of the results within 7 days. Patients with a positive HRG status, defined as HRG ISH score of  $\geq 1+$ , will be eligible for randomization.

Prior to receiving the first dose, all HRG positive patients that receive HRG results for eligibility based on testing of archived samples will also be asked to undergo a fresh research biopsy, prior to first dose. An additional sample will not be requested from patients who underwent a fresh biopsy for eligibility testing. The sample should be collected and processed according to the laboratory manual.

Once all screening procedures have been completed and eligibility for treatment randomization (including HRG positive ISH result) has been determined, the investigator may randomize the patient. Patients will be randomized in a 1:1 ratio (experimental arm versus comparator arm) using an Interactive Web Response System (IWRS). Randomization will be stratified based on bone-only disease (yes, no) and geographic region (US, non-US). Patients will be assigned to Arm A or Arm B:

#### Arm A (Experimental Arm):

Seribantumab: fixed dose of 3000 mg intravenously (IV) on day 1 and 15 of each 28-day cycle

Fulvestrant: 500 mg intramuscularly (IM) on Days 1 and 15 of Cycle 1, and then on Day 1 of each subsequent 28 day cycle

### Arm B (Control Arm):

Placebo: intravenously (IV) on day 1 and 15 of each 28-day cycle Fulvestrant: 500 mg intramuscularly (IM) on Days 1 and 15 of Cycle 1, and then on Day 1 of each subsequent 28 day cycle

Treatment will start within 7 days following randomization. It is intended that patients will be treated until investigator-assessed disease progression or unacceptable toxicity, whichever comes first. Tumor assessments will be measured and recorded by the local radiologist every 8 weeks (±5 days) from randomization using RECIST guidelines (version 1.1). Tumor assessments will be performed every 8 weeks, regardless of dose delays or dose interruptions, until investigator-assessed PD. Patients who come off study treatment prior to disease progression for reasons including patient or physician decision or unacceptable toxicity will continue to undergo tumor assessments every 8 weeks (±5 days) until investigator assessed PD. Patients will be treated according to local assessment of tumor scans.

All patients will have a follow-up visit scheduled 30 days (±7 days) after the last dose of study treatment, regardless of reason for treatment termination. Patients will not be allowed to cross over from placebo to seribantumab. Survival follow up will be required for all patients every 2 months from the 30-day follow-up visit until death, loss to follow-up, withdrawal of consent, or study termination. After patients discontinue study treatment, subsequent

	anti-cancer therapies will be collected according to the same schedule at the same time as survival follow-up.						
	An independent Data Monitoring Committee (DMC) will be established						
	monitor emerging safety data and evaluate for trial efficacy. The DMG						
	regularly monitor safety data over the course of the study in accordance with						
	the DMC Charter.						
ESTIMATED # OF	Approximately 200 patients will be screened to enroll 80 HRG+ patients						
PATIENTS:	from an estimated 60-80 clinical trial sites from North America and Europe.  Women with metastatic ER/PR positive, HER2 negative, HRG positive						
	breast cancer that has progressed following systemic therapy with a CDK						
	inhibitor (e.g. palbociclib) in the locally advanced or metastatic disease						
CTUDY DODIN ATION	setting. Patients cannot have received more than a total of two prior lines of						
STUDY POPULATION	therapy in the locally advanced or metastatic disease setting, and patients						

	o Patients with bone-only lesions who have received radiation to those lesions must have documented progression following radiation						
	therapy.						
	Able to understand and sign an informed consent (or have a legal						
	representative who is able to do so)						
	• ECOG Performance Score (PS) of 0 or 1						
	Adequate bone marrow reserves as evidenced by:						
	$\circ  \widehat{ANC} > 1500/\mu l$						
	
 
Platelet count > 100,000/μl; and
 
						
	○ Hemoglobin > 9 g/dL						
	Adequate hepatic function as evidenced by:						

	·
	o Serum total bilirubin $\leq 1.5$ x ULN except for patients with Morbus Gilbert
	
 
Aspartate aminotransferase (AST), Alanine aminotransferase (ALT)
 

	and Alkaline Phosphatase $\leq 2.5 \times \text{ULN} (\leq 5 \times \text{ULN is acceptable if})$
	liver metastases are present, and $\leq 5 \times ULN$ of Alkaline Phosphatase
	is acceptable if bone metastases are present)
	
 
Adequate renal function as evidenced by a serum creatinine ≤ 1.5 x ULN
 

	• Recovered from clinically significant effects of any prior surgery, radiotherapy, or other antineoplastic therapy.
	
 
Patients may be treated with bone modifying agents such as
 

	bisphosphonates or receptor activator of nuclear factor kappa-B
	(RANK)-ligand agents (e.g. denosumab) per American Society of
	Clinical Oncology (ASCO) guidelines; whenever possible, patients
	requiring bone modifying agents should start treatment $\geq 7$ days prior to
	study therapy and should continue the same agent throughout study
	unless clinically compelled to change
	• $\geq$ 18 years of age
	Patients who have experienced a venous thromboembolic event within
	60 days of signing the main consent form should have been treated with
	anti-coagulants for at least 7 days prior to beginning treatment and for
	the duration of treatment on this study.
	Patients must meet all the inclusion criteria listed above and none of the
	following exclusion criteria:
	
 
Prior treatment with an anti-ErbB3 antibody
 

	
 
Prior treatment with a chemotherapy in the locally advanced or
 

	metastatic disease setting
	• Patients cannot have received prior fulvestrant or other SERDs in the
	locally advanced or metastatic setting
	• Uncontrolled CNS disease or presence of leptomeningeal disease
	
 
Inflammatory breast cancer
 

	• History of another active malignancy that required systemic therapy in
	the last 2 years. Patients with prior history of in-situ cancer or basal or
ENGLICION	squamous cell skin cancer are eligible.
EXCLUSION	• Active infection, or an unexplained fever > 38.5°C during screening
CRITERIA:	visits or on the first scheduled day of dosing, which in the investigator's
	opinion might compromise the patient's participation in the trial or
	affect the study outcome. At the discretion of the investigator, patients
	with tumor fever may be enrolled
	Known hypersensitivity to any of the components of seribantumab,  fully extremt, or who have had hypersensitivity reactions to fully hypersensitivity reactions.
	fulvestrant, or who have had hypersensitivity reactions to fully human monoclonal antibodies
	
 
Received other recent antitumor therapy including:
 

	• Received other recent annumor therapy including.  • Investigational therapy administered within the 28 days or 5
	half-lives, whichever is shorter, prior to the first scheduled day
	of dosing in this study
	
 
Radiation or other standard systemic therapy within 14 days
 

	prior to the first scheduled dose in this study, including, in
	prior to the first senegative dose in this study, including, in

	addition (if necessary), the timeframe for resolution of any
	actual or anticipated toxicities from such radiation
	NYHA Class III or IV congestive heart failure
	Patients with a significant history of cardiac disease (i.e. uncontrolled
	blood pressure, unstable angina, myocardial infarction within 1 year or
	ventricular arrhythmias requiring medication) are also excluded
	Uncontrolled infection requiring IV antibiotics, antivirals, or     set if you gally an active hymner improve a deficiency view (IIV) infection.
	antifungals; or active human immunodeficiency virus (HIV) infection,
	
 
active hepatitis B infection or active hepatitis C infection
 
Any other medical condition deemed by the Investigator to be likely to
 

	• Any other medical condition deemed by the Investigator to be likely to interfere with a patient's ability to sign informed consent, interfere with
	a patient's ability to cooperate and participate in the study, or interfere
	with the interpretation of the results
	A total study duration of approximately 20 months is expected.
LENGTH OF STUDY:	The primary analysis will be initiated when 58 PFS events have occurred.
STUDY	
TREATMENT(S):	Seribantumab/fulvestrant or placebo/fulvestrant (1:1)
INVESTIGATIONAL	Seribantumab is a clear liquid, supplied in sterile, single-use vials at a
PRODUCT(S)	concentration of 25 mg/mL in 20 mM histidine, 150 mM sodium chloride,
FORMULATION:	and pH 6.5. Seribantumab should be stored at 2-8°C.
ROUTE(S) OF	Seribantumab for intravenous (IV) infusion over 1 hour
ADMINISTRATION:	
NON	Fulvestrant solution for intramuscular injection (50 mg/mL) is commercially
NON INVESTIGATIONAL	available. Fulvestrant is stored refrigerated at 2°-8°C (36°-46°F).
PRODUCT	Placebo: A clear liquid, supplied in sterile, single-use vials at a containing
FORMULATION:	20 mM histidine, 150 mM sodium chloride, at a pH of 6.5. Placebo should
TORMULATION.	be stored at 2-8°C.
ROUTE(S) OF	Seribantumab and placebo: intravenous (IV) infusion over one hour
ADMINISTRATION:	Fulvestrant: intramuscular (IM) injection
	Seribantumab 3 gm or matched placebo (120 mL) will be administered by
DOSE REGIMEN:	intravenous infusion over 60 minutes on Days 1 and 15 of a 28 day cycle.
DUSE REGIMEN:	Fulvestrant 500 mg will be administered intramuscularly on Days 1 and 15,
	and then Day 1 of each subsequent 28 day cycle.
	The median PFS for the control arm (fulvestrant + placebo) is assumed to be
	4.0 months in this patient population. A total of 58 PFS events will be
	required across two treatment arms randomized in a 1:1 ratio, giving
	approximately 80% power to detect a true hazard ratio of HR $\leq$ 0.57 (mPFS:
	4 v 7), assuming a 1-sided significance level of 0.10. Approximately 200
	patients will need to be screened in order to accrue 80 randomized in
SAMPLE	approximately 16 months with a total duration of 20 months.
SIZE/STATISTICAL	Primary Efficacy and Key Secondary Analysis:
CONSIDERATIONS:	The primary efficacy analysis will be performed using the Per Protocol (PP)
	population. PFS is defined as the number of months from the date of
	randomization to the date of the first documented objective disease
	progression (PD) using RECIST v1.1 or death due to any cause, whichever
	occurs first. If neither death nor progression is observed, data will be
	censored on the date of the last observed tumor assessment date. Patients
	without a valid tumor response evaluation at randomization will be censored

[figure not shown]

on the date of randomization. Patients starting a new anti-cancer treatment prior to documented PD will be censored at the date of the last observed tumor assessment prior to start of the new treatment. Patients with documented PD or death after an unacceptable long interval (i.e., 2 or more missed or indeterminate scheduled assessments) will be censored at the time of the last observed tumor assessment date. PFS will be calculated as the date of the event/censor minus date of randomization plus one.

The primary analysis will be performed using a stratified log-rank test comparing the PFS difference between two treatment arms. The final PFS analysis will preserve the 1-sided alpha at 0.10. Stratification factors will include bone-only disease (yes, no) and geographic status (US, and non-US). Kaplan-Meier estimates will be used to display PFS time graphically. Cox proportional hazards model will be used to estimate hazard ratio and the corresponding 80% confidence interval. Median PFS event times and 80% confidence interval will be computed as well.

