### 10.5. Efficacy Analysis

### 10.5.1. Primary Efficacy Analysis

PFS is defined as the time from randomization to the first documented radiographical progression of disease using RECIST v1.1 or death from any cause, whichever comes first. Details of censorship will be thoroughly explained in the SAP. PFS will be analyzed based on investigator assessed. The primary endpoint will be based on the investigator assessment of disease progression.

The Kaplan-Meier estimates will be used to determine median PFS and 80% CI for each treatment group. A stratified log-rank will be used to test for PFS distribution differences. A stratified Cox proportional hazards model will be used to estimate the hazard ratio and corresponding 80% confidence intervals. Stratification factors include: Geographic region (US, non-US) and bone-only disease (yes, no).

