## **3. ENDPOINTS**

## 3.1 Progression-Free Survival – Investigator Assessed

Investigator Assessed (IA) tumors assessments are those determined by the investigator. PFS is defined as the number of months from the date of randomization to the date of death or documented (objective) disease progression via RECISTv1.1, whichever occurs earliest. Length of PFS will be calculated in days and reported in months.

[Progression/Death/Censor Date - Randomization Date + 1] / 30.4375.

The tumor assessment (i.e., scan dates) will be used for progression/censor date not the date corresponding to the determination of overall response. When multiple dates occur for assessing target, non-target, and new lesions the following rule will be applied:

- If documented disease progressions, the *first* available date will define the tumor assessment date
- If censored, the *last* available date will define the tumor assessment date.

Per protocol tumor assessments are scheduled to be performed every 8 weeks ( $\pm$  7 days) from day of first dose until investigator-assessed progression, in addition to a 30-day follow-up.

**Censorship**: In general, patients are censored at the date of the last tumor assessment that verified lack of disease progression if they are last known to be alive, on-treatment or within 30 days following treatment discontinuation, and progression-free. Censoring is explicitly described below and in table 1. Patients that do not experience progression or death by the time of analysis (data cut-off) will be censored at the date of last tumor assessment defined by any overall response other than "not evaluable".

- Patients with an inadequate/incomplete baseline tumor assessment will be censored at the date of randomization
- Patients with no tumor assessment after dosing will be censored at the date of randomization unless death occurred prior to the first planned assessment (in which case the death is an event)
- Patients with at least one on-study disease assessment who discontinue treatment without documented disease progression or death are censored at the date of the last tumor assessment

There are two exceptions.

- $\circ$  Documented progression or death  $\leq$  30 days after treatment discontinuation then progression or death is an event

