- A new anti-cancer treatment is started prior to documented progression and ≤ 30 days after treatment discontinuation, then censorship is at the date of the last tumor assessment that verified lack of disease progression prior to the new treatment
- Patients with documentation of progression or death after an unacceptably long interval (i.e., 2 or more consecutively missed or indeterminate/not evaluable assessments) since the last tumor assessment will be censored at the date of last tumor assessment documenting no progression

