#### Table 3.1 Documented Disease Progression and Censoring

Situation	Date of	Outcome
Inadequate baseline tumor assessment No on-treatment assessment and no death prior to first scheduled assessment	Randomization	Censored
Death or documented disease progression after ≥ 2 consecutively missed and/or not evaluable scheduled tumor assessments	Last tumor assessment documenting no disease progression	Censored
Alive, on-treatment, and no documented disease progression	Last tumor assessment documenting no disease progression	
Documented disease progression (on, prior to, or $\leq 30$ days after treatment discontinuation)	First tumor assessment documenting disease progression	Progression (Event)
New anticancer treatment $\leq$ 30 days after treatment discontinuation without disease progression	Last tumor assessment documenting no disease progression prior to starting the new anticancer treatment	Censored
Treatment discontinuation due to toxicity, undocumented disease progression, or any other reason	Last tumor assessment documenting no disease progression prior to discontinuation	Censored
Death prior to first scheduled assessment	Death	Death (Event)
Death without documented disease progression and $\leq 30$ days after treatment discontinuation	Death	Death (Event)

Note: Follow-up scans can be performed up to 4 weeks from last treatment dose date via protocol

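### The synopsis rule for primary PFS after missed scans lets an indeterminate scan set the censor date and does not say whether the missed scans must be consecutive; the supplied SAP differs on both (minor)

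*Protocol*

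**What the plan says.** **Protocol, Study Synopsis (Sample Size/Statistical Considerations).** The rule opens with "Patients with documented PD or death after an unacceptable long interval" and defines that interval as "2 or more missed or indeterminate scheduled assessments) will be censored at the time of the last observed tumor assessment date". The word consecutive does not appear, and the censoring scan need not be evaluable or progression-free. The synopsis also uses the last observed assessment for patients with neither progression nor death, and for those who start new anti-cancer treatment (there limited to scans before that treatment).

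**SAP, section 3.1.** The corresponding rule requires "2 or more consecutively missed or indeterminate/not evaluable assessments) since the last tumor assessment" and says the patient is "censored at the date of last tumor assessment documenting no progression". Table 3.1 repeats the trigger as "consecutively missed and/or not evaluable scheduled tumor assessments". The general rule in the same section bars a not-evaluable assessment from setting the censor date.

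**Which text governs.** Protocol 10.5.1 gives no censoring rule of its own and says: "Details of censorship will be thoroughly explained in the SAP". Protocol section 10 lets the SAP modify the plan, but requires major changes to the primary endpoint or its analysis to appear in a protocol amendment. The supplied SAP names protocol seribantumab-02-03-10 (section 1), a phase 3 trial with exemestane or fulvestrant (1.2), 2:1 allocation, 195 events and one-sided 0.025 (5.1). This protocol is MM-121-02-02-10: phase 2, fulvestrant only, 1:1, 58 events, one-sided 0.10.

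**The concern.** The rule decides which progressions and deaths count as primary events and how long the other patients are credited as progression-free. The two texts differ on the trigger and on the date, and neither document reconciles them. Two programmers could build different primary datasets from the same scans.

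The date matters because an indeterminate scan says nothing about progression. If it sets the censor date, the patient stays in the risk set over weeks in which her status was unknown, and the rule applies to patients known to have progressed or died by the next informative observation. The trigger matters because missed scans accumulate with time on study, so a count that need not be consecutive would remove later events, somewhat more often on the arm with longer PFS. The rule also affects when the trial reads out, since the primary analysis starts at 58 PFS events (Synopsis, Length of Study).

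**Working it through.** **1. The plan's own figure.** Inputs from Protocol 10.2: HR 0.57 (medians 4 and 7 months), one-sided 0.10, 80% power, 1:1. Schoenfeld: d = 4(z₀.₁₀ + z₀.₂₀)² / (ln HR)² = 4(1.2816 + 0.8416)² / 0.5621² = 18.03 / 0.316 = 57.1, rounded up to 58. Power at 58 events is 80.5%. The event calculation is sound, and this point does not touch it.

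**2. Censor date.** Scans are every 8 weeks (Protocol 7.7). PFS time is (date − randomization + 1) / 30.4375 (SAP 3.1). Take a patient clean at week 8, indeterminate at weeks 16 and 24, with progression at week 32. Both texts censor her.
- SAP, last scan documenting no progression (week 8): (56 + 1) / 30.4375 = 1.9 months.
- Synopsis, last observed scan before the progression scan (week 24): (168 + 1) / 30.4375 = 5.6 months.
- Difference: 112 / 30.4375 = 3.7 months, against an assumed control median of 4.0 months.

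This holds even if the last observed scan is taken to mean the last one before progression. If weeks 16 and 24 were missed rather than indeterminate, that reading gives week 8 in both texts, so the firm difference is confined to indeterminate scans.

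**3. Trigger.** Take a patient clean at week 8, missed at week 16, clean at week 24, indeterminate at week 32, with progression at week 40. The SAP counts an event at (280 + 1) / 30.4375 = 9.2 months. The synopsis definition, taken literally, censors her: two lost scans in total, though not consecutive.

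For a sense of scale, take six scheduled scans before progression, each lost independently with probability 10%:
- P(2 or more lost in total) = 1 − 0.9⁶ − 6(0.1)(0.9⁵) = 11.4%
- P(the last two both lost) = 0.1² = 1.0%

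**4. Size of the trigger difference.** The documents give no scan-loss rate, so 5% to 20% per scan is an assumption. First, exponential PFS with medians 4 and 7 months, 8-weekly scans, independent losses and progression detected within 20 months of each patient's randomization. Progressions censored per 58, arms averaged:

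| Loss per scan | Two in total | Two consecutive, just before the event |
|---|---|---|
| 5% | 1.1 | 0.3 |
| 10% | 3.7 | 1.2 |
| 15% | 7.2 | 2.7 |
| 20% | 11.1 | 4.6 |

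At 10% the literal count censors 7.5% of progressions in the 7-month arm and 5.3% in the 4-month arm; the consecutive rule censors 2.1% in each.

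Second, the trial as planned: 80 patients, 16 months' accrual, cut when the consecutive rule has 58 events. Follow-up is shorter, so the gap is smaller. The literal trigger then leaves 57.6, 56.5, 55.0 and 53.0 events at 5, 10, 15 and 20% loss. At 10% that is 58 − 56.5 = 1.5 events fewer.

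**5. Power and timing.** The analysis waits for 58 events under whichever rule is used. With the literal trigger, censoring at the previous observed scan and a cut at 58 events under that rule, power (consecutive v literal) was 81.3 v 81.3% at 10% loss, 80.1 v 80.2% at 15% and 79.9 v 80.7% at 20%. A separate run at 10% gave 80.0 v 79.7%. These differences are within simulation noise of about a point. The cost is time: about 0.7, 2.2 and 4.6 months at 10, 15 and 20% loss, against a planned duration of 20 months. At 20%, about 30% of simulated trials never reached 58 events.

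**The case against.** **The SAP is the place for this detail.** Protocol 10.5.1 says so, and a synopsis made precise in a SAP is ordinary practice. That would settle the matter if the supplied SAP belonged to this trial. It describes a different one, so the synopsis holds the only missed-scan rule written for this protocol. The mismatched SAP is the larger defect, and this difference is one consequence of it.

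**The protocol probably meant consecutive scans.** A reader might infer that the protocol drops an event after any two missed scans. The documents do not support stating that as its rule: the operative condition is an overlong interval, and in the week-40 example the event follows one ordinary 8-week interval. This objection largely stands. What remains is that the i.e. definition omits the word, so the trigger is ambiguous.

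**Censoring at the progression scan.** A reader might take the last observed assessment to be the progression scan itself. Nothing excludes it, but it is strained: the preceding synopsis sentence, on new treatment, uses the phrase to look back. It is not relied on here.

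**Loss of power.** A reader might infer that the synopsis rule erodes the stated 80%. Simulated losses, such as 79.2 to 77.6% at 10% scan loss or 80.0 to 73.2% at 20%, appear only when the literal trigger is combined with censoring at the progression scan and the cut is fixed at 58 events under the SAP rule. Without those choices the loss disappears.

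**The planned sensitivity analysis covers it.** Protocol 10.5.2 declares all censored patients as events. That would bring back the events this rule removes, but it is a sensitivity analysis and does not settle the primary rule or its censor date.

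**Conclusion.** The point holds as a minor defect. What is firm is the censor date: the synopsis allows an indeterminate scan to set it, which in the worked example credits 3.7 months of undocumented progression-free time. The trigger is unclear and may be loose drafting.

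The effect on the trial is probably small. On the first set of simulated figures, a 10% loss rate exposes about 1.2 of 58 progressions to the long-interval rule if scans must be consecutive and 3.7 if not; only those with an indeterminate scan after the last clean one would carry the firm date difference. At 5% loss or less the effect of the trigger is negligible. At about 10% the literal trigger removes about 1.5 of 58 events at a fixed cut, which in an event-driven analysis becomes about 0.7 months of delay. Larger delays need loss rates of 15% or more. All of this rests on an assumed loss rate, independent losses and exponential PFS. A loss of power is not established, and the 58-event calculation stands.

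**What to change.** Put one rule, in the same words, in the synopsis and in a SAP written for this trial:

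- Progression or death immediately after two or more consecutive missed or not-evaluable scheduled assessments is censored at the last evaluable assessment documenting no progression before the gap.
- Wherever other PFS censoring falls back on the last scan (no event by the cut-off, or new anti-cancer treatment), use the last evaluable assessment documenting no progression, keeping the existing limit to scans before the new treatment.

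Do this before unblinding, since choosing later between two written rules for the primary endpoint would be a post hoc choice. The cost is about two lines of wording, with no new data and no change to study conduct.
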